**Table 2: Dose Modification Guidelines for Avapritinib-related Toxicity**

Toxicity	Modification
General	
Grade 1 or Grade 2	
 
• No dose modification required
 

Grade 3 - 4	
 
• Occurrence: Hold until event is <math>\leq</math> Grade 2, or has returned to baseline, and then resume by reducing the dose by 100 mg less than the current dose 
 
◦
 
 
 
• Occurrence at 100 mg: Discontinue avapritinib 
 
◦
 
 
 

Cognitive or Mood Effects	
Grade 1 with only minor impairment	No dose modification required
Grade 1, other than minor impairment	
 
• Interrupt dosing for 7 days, and resume dosing without dose reduction
 
• The dosing interruption may be repeated if the impairment continues to worsen after resuming dosing; however, repeated dosing interruption is at the discretion of the investigator, and should be balanced with the need to treat the underlying GIST
 

Grade 2	
 
• Interrupt dosing for a minimum of 7 days
 
• Resume dosing with a dose reduction of 100 mg when the cognitive effect has improved to Grade 1 or less, or still at Grade 2, if continued treatment is considered in the best medical interest of the patient due to the underlying GIST
 
• If the patient is already receiving a dose of 100 mg QD, and continued treatment is considered in the best medical interest of the patient due to the underlying GIST, treatment may be resumed at 100 mg
 

Grade 3-4	
 
• Interrupt dosing for a minimum of 14 days
 
• Resume dosing with a dose reduction of 100 mg when the cognitive effect has improved to Grade 1 or less, or when it has improved to Grade 2, if continued treatment is considered in the best medical interest of the patient due to the underlying GIST
 
• Occurrence at 100 mg: Discontinue avapritinib
 

Intracranial Bleeding	
Grade 1-4	
 
• Discontinue avapritinib
 

Abbreviations: CNS = central nervous system; GIST = gastrointestinal stromal tumor; QD = once daily.

 Changes in cognition, memory, attention, mood, or speech (thought to originate in the CNS). If avapritinib treatment is resumed after interruption for a cognitive or mood effect, or for an intracranial bleeding event, the investigator must document in writing that resuming avapritinib treatment was considered to be in the best medical interest of the patient.

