#### 4.2 Selection of Patients

Patients must meet the inclusion and exclusion criteria to be enrolled in the trial. The Sponsor will consider inclusion of patients who do not meet the inclusion and exclusion criteria on a case by case basis following receipt of supporting information and rationale from the Investigator. Such exceptions may also require approval by the Independent Ethics Committee (IEC), as appropriate.

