#### **4.4 Exclusion Criteria**

Patients meeting any of the following criteria will not be eligible for Study participation:

1. Patient requires therapy with a concomitant medication that is a strong inhibitor or strong inducer of cytochrome P450 (CYP) 3A4 (see [Section 5.4.1](#)).
2. Patient has a history of intracranial bleeding either prior to or during avapritinib treatment
3. Patients who have poor organ function, defined as Adverse Events of NCI CTCAE version 5.0 Grade 3 or higher at the time of enrollment must delay start of treatment until symptoms return to Grade 2 or baseline, or the start of treatment has been approved by the Sponsor.
4. Patients who have ongoing cognitive or mood effects Adverse Events of NCI CTCAE version 5.0 higher than Grade 1 must delay start of treatment until symptoms return to Grade 1 or baseline.
5. Women who are unwilling, if not postmenopausal or surgically sterile, to abstain from sexual intercourse or employ highly effective contraception from the time of enrollment and for at least 30 days after the last dose of avapritinib. Men who are unwilling, if not surgically sterile, to abstain from sexual intercourse or employ highly effective contraception from the time of first dose and for at least 90 days after the last dose of avapritinib. Refer to [Section 5.5.1](#) for acceptable methods of contraception.
6. Women who are pregnant, as documented by a serum beta human chorionic gonadotropin ( $\beta$ -hCG) pregnancy test consistent with pregnancy, obtained within 7 days before the enrollment. Females with  $\beta$ -hCG values that are within the range for pregnancy but are not pregnant (false-positives) may be enrolled with written consent of the Sponsor, after pregnancy has been ruled out. Females of non-childbearing potential (postmenopausal for more than 1 year; bilateral tubal ligation; bilateral oophorectomy; hysterectomy) do not require a serum  $\beta$ -hCG test.
7. Women who are breast feeding.
8. Patients with a known hypersensitivity to avapritinib or the excipients.

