## 4.6 Patient Withdrawal Criteria

Patients have the right to withdraw from the Study at any time for any reason.

Patients must withdraw or be withdrawn from Study treatment for any of the following reasons:

- Withdrawal of consent;
- Pregnancy;
- Death.

Patients may withdraw or be withdrawn from Study treatment for any of the following reasons:

- AE;
- Disease progression;
- Protocol deviation;
- Investigator decision;
- Loss to follow-up.

When a patient discontinues Study drug, the primary reason(s) for discontinuation is to be recorded in the case report form (CRF). Following discontinuation of Study drug, all efforts will be made to complete and report the protocol-defined Study observations as completely as possible.

If a patient discontinues treatment because of an adverse event (AE), protocol-specified safety follow-up is to be performed, and the patient should remain under the supervision of the Investigator or designee until the condition has returned to baseline or stabilized.

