## 5.3 Dose and Administration

Avapritinib will be administered PO at the dose received by the patient on the prior avapritinib protocol in continuous 28-day cycles. Dosing will be continuous, with no inter-cycle rest periods unless warranted for individual safety reasons. Pre-specified dose modification recommendations for AEs related to avapritinib are described in [Section 5.3.1](#).

Avapritinib should be administered with a glass of water (at least 8 ounces or 250 mL). The tablets should be taken on an empty stomach at least 1 hour before or least 2 hours after a meal. Each dose should be administered at approximately the same time each day. Do not make up for a missed dose within 8 hours of the next scheduled dose. If a patient vomits during or after taking avapritinib, the dose should not be replaced, and the next dose should be taken at the next scheduled dosing time.

Patients should be instructed to swallow tablets whole and to not chew the tablets. Interruption in avapritinib dosing may be required for surgery or other procedure during the treatment period. At a minimum, avapritinib should be discontinued 48 hours before the procedure and resumed 48 hours after the procedure is completed.

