### 5.3.1 Dose Reduction for Adverse Events

Dosing modifications are recommended for patients experiencing avapritinib-related toxicity. Modification guidelines are summarized in [Table 2](#).

If a patient experiences a Grade 3 or worse (based on NCI CTCAE criteria) AE thought to be caused by avapritinib, avapritinib treatment should be interrupted until the AE improves to Grade 2 or to the patient's baseline, or it is considered stable, and does not preclude continued therapy. At that time, avapritinib treatment may resume either at the same dose, or at reduced dose. Dose reductions should be in increments of 100 mg. If a Grade 3 or worse AE recurs, dosing should be interrupted as described above, and if dosing is resumed, the dose should be reduced by at least 100 mg.

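### Table 2 says to discontinue avapritinib after an intracranial bleed of Grade 1-4, but the footnote on that same heading provides for restarting it

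*Combined protocol and SAP*

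**What the plan says.** Table 2 in Section 5.3.1 has three blocks: general toxicity, cognitive or mood effects, and intracranial bleeding. The bleeding block has a single row covering Grades 1 to 4, and its whole content is "Discontinue avapritinib".

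The headings of the cognitive block and the bleeding block both carry footnote 2. It opens "If avapritinib treatment is resumed after interruption for a cognitive or mood effect, or for an intracranial bleeding event" and continues that "the investigator must document in writing that resuming avapritinib treatment was considered to be in the best medical interest of the patient".

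Other text that bears on the point:

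- **Section 5.3.1, paragraph on Grade 3 or worse related events.** Dosing is interrupted until the event improves, returns to baseline or is stable and does not rule out further therapy. Then "At that time, avapritinib treatment may resume either at the same dose, or at reduced dose". Intracranial bleeding is not mentioned.
- **Section 5.5.** A patient at increased risk of intracranial bleeding, for example after a bleed in the past year, should receive avapritinib only if the expected benefit outweighs that added risk.
- **Section 4.4, exclusion 2.** Entry is barred if the "Patient has a history of intracranial bleeding either prior to or during avapritinib treatment".
- **Section 9.3.** Intracranial bleeding is one of the two categories of adverse event of special interest.

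**The concern.** A row and the footnote attached to it should give one instruction. Here the row ends treatment and the footnote describes how treatment is restarted. The conflict concerns a harm that Section 5.5 acknowledges has occurred in patients taking this drug.

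What is at stake is mainly patient safety: whether someone who has bled into the head on study drug is exposed to it again. That would depend on which line the investigator reads, not on a rule the sponsor has set. There is a smaller effect on the data. Section 10 promises the reasons for treatment discontinuation and a descriptive summary of treatment duration, and both depend on how the bleed was handled.

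**Working it through.** The plan states no figure on this point, so the check is mainly a comparison of texts.

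**Step 1. What the row means alone.** Elsewhere Table 2 tells the investigator to hold or interrupt when a restart is foreseen, and then says how to resume. The general Grade 3-4 row does this, as do the cognitive rows from Grade 1 beyond minor impairment upward. The bleeding row has no hold, no interval and no resume step. It uses the same verb as the two rules for a Grade 3-4 event in a patient already at 100 mg, which also have no resume step. Within the table, the natural reading is a permanent stop.

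**Step 2. What the footnote means alone.** It names the bleeding event, calls the stop an interruption, and sets a documentation duty for resuming. For cognitive effects this fits, because those rows contain interruptions. For bleeding no row contains one.

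**Step 3. Whether other text settles it.**

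| Text | Bearing on a bleed | Settles the conflict? |
|---|---|---|
| Section 5.3.1, Grade 3 or worse paragraph | General rule for related events; no exception for bleeding | No. Silent on Grades 1-2, and the specific row can be read as overriding it |
| Section 5.3, procedures | "avapritinib should be discontinued 48 hours before the procedure and resumed 48 hours after the procedure is completed" | No. Shows that the verb is also used for a pause, but there the restart is stated in the same sentence |
| Section 5.5 | Benefit must exceed added risk; not limited to entry | No. Adds a condition on any restart without saying whether restart is allowed |
| Section 4.4, exclusion 2 | Bars entry after a bleed, including one during avapritinib | No. Governs entry only, though it fits a permanent stop better than a restart |

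The conflict therefore lies between the row and footnote 2, for all of Grades 1 to 4, and nothing else in the protocol resolves it.

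**Step 4. How often it could arise.** Section 4.1 plans about 5 patients. The documents give no incidence of intracranial bleeding, so the per-patient risk p is assumed. With independent patients, P(at least one bleed) = 1 − (1 − p)^5:

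- p = 0.01: 1 − 0.99^5 = 0.049
- p = 0.03: 1 − 0.97^5 = 0.141
- p = 0.05: 1 − 0.95^5 = 0.226

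This is the chance that the rule is needed at all. It is not the chance that a patient is re-exposed.

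**The case against.** The best defence is that the two texts can be reconciled. Table 2 is headed as guidelines and Section 5.3.1 calls its modifications recommended. Footnote 2 is conditional. On that view discontinuation is the default, and the footnote only obliges an investigator who departs from it to justify the departure in writing, with Section 5.5 adding a benefit-risk test. This is a possible reading, and it means the sponsor's intention cannot be known from the text. It does not remove the problem: the row does not present itself as a default, and the footnote speaks of an interruption that the row never offers. If a restart route was intended, its conditions have not been written.

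A reader might infer several stronger things, and the documents do not support them:

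- **That Section 5.3.1 independently permits a same-dose restart after a bleed.** Its paragraph is general and covers only Grade 3 or worse related events. Its same-dose option also differs from the general Grade 3-4 row, which requires a 100 mg reduction, so that mismatch is not specific to bleeding.
- **That Section 4.6 contradicts the row.** Adverse events do fall under "Patients may withdraw or be withdrawn from Study treatment for any of the following reasons", but the mandatory list there contains no toxicity stop of any kind. The other discontinuation rules in Table 2 are absent from it too.
- **That the protocol permits restart without the sponsor's agreement.** This rests on silence. No Table 2 modification asks for sponsor agreement.
- **That restart conditions after a bleed are weaker than after a cognitive effect.** The bleeding row gives no minimum time off or dose reduction because its action is to stop. Treating those blanks as zeros compares a stop rule with a restart schedule, and overlooks Section 5.5.
- **That Sections 4.4 and 5.5 conflict.** The first governs entry and the second adds a condition on treatment. A patient with a past bleed could still enter, since "The Sponsor will consider inclusion of patients who do not meet the inclusion and exclusion criteria on a case by case basis".

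**Conclusion.** The point holds as an internal inconsistency between the Table 2 bleeding row and footnote 2, and it should be corrected. It rests on current protocol text: the footnote mark sits on the bleeding heading and the footnote names the event. The conclusion does not depend on any assumed bleeding rate.

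Its practical size is limited. With about 5 patients, a bleed on study has a chance of 4.9% to 22.6% if the per-patient risk is between 1% and 5%, a range that is assumed because the documents give none. The effect on the Section 10 summaries is minor, since they are descriptive and no hypothesis is tested. The reason to act is that, if a bleed does occur, the protocol does not settle whether the patient may be given the drug again.

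**What to change.** Write one rule.

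1. In Table 2, reword the bleeding row as *Grade 1-4: permanently discontinue avapritinib*.
2. Remove mark 2 from the intracranial bleeding heading, and delete from footnote 2 the clause that refers to a bleeding event. The footnote then applies to cognitive and mood effects only.
3. For clarity, add to the Grade 3 or worse paragraph in Section 5.3.1: *except intracranial bleeding, see Table 2*.

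If the sponsor does intend a restart route, the row itself should state it with explicit conditions, for example the highest grade allowed, the minimum time off, the dose on resuming and whose agreement is needed.

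Listing intracranial bleeding among the mandatory withdrawals in Section 4.6, or cross-referring Sections 4.4 and 5.5, is optional drafting and not needed to correct the error.

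The cost is one text amendment under Section 13, with ethics committee approval, and no new visit, test or data item. The drawback is that a patient with a Grade 1 bleed who is still benefiting would stop study drug, which is what the row already directs.

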## 5.4 Prior and Concomitant Therapy

### 5.4.1 Prohibited Concomitant Therapy

Concomitant treatment with drugs that are strong CYP3A4 inhibitors are prohibited (refer to [Appendix 1](#) for a list of strong CYP3A4 inhibitors).

Avapritinib should not be administered simultaneously with other antineoplastic therapy.

If radiotherapy is required to treat local sites of disease, avapritinib treatment should be interrupted for 2 days prior to the first fraction of radiotherapy through 2 days after the last fraction.

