#### **5.4.2     *Concomitant Therapy to be used with Caution***

Medications that are CYP2C9, CYP3A4, or BCRP substrates with a narrow therapeutic index should be used with caution (Refer to [Appendix 2](#) for a list of these medications).

In addition, medications that are known to increase the risk of seizures should be used with caution.

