#### **5.4.3     *Permitted Concomitant Therapy***

Medications and treatments other than those specified in [Section 5.4.1](#) and [Section 5.4.2](#), including palliative and supportive care for disease-related symptoms are permitted.

Patients should be closely monitored, and treatment is to be instituted for disease-related symptoms as appropriate. Supportive care measures for treating AEs should be instituted as soon as they are recognized.

Anti-emetic treatments may be used at the Investigator's discretion and in accordance with the American Society of Clinical Oncology guidelines or equivalent after documented nausea or vomiting has occurred without medications having been used. The choice of anti-emetic treatment, if required, will be made at the Investigator's discretion. Prophylaxis for nausea, vomiting, and diarrhea may be given as needed.

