## **18 APPENDICES**

**18.1 Appendix 1: List of Prohibited Medications and Food****EXCLUDED MEDICATIONS AND FOODS FOR PATIENTS RECEIVING  
AVAPRITINIB**

Strong CYP3A4 Inhibitors	Strong CYP3A4 Inducers	Moderate CYP3A4 Inducers
Boceprevir	Carbamazepine	Bosentan
Clarithromycin	Phenytoin	Efavirenz
Cobicistat	Rifampin	Etravirine
Conivaptan	St. John's Wort	Modafinil
Grapefruit, grapefruit juice	Phenobarbital	Dabrafenib
Indinavir		
Itraconazole		
Ketoconazole		
Lopinavir		
Nefazodone		
Nelfinavir		
Posaconazole		
Ritonavir		
Saquinavir		
Telaprevir		
Telithromycin		
Voriconazole		

Abbreviations: CYP3A4 = cytochrome P450 3A4.

This list is not intended to be exhaustive. A similar restriction will apply to other drugs that are known to strongly modulate CYP3A4 via inhibition or induction or are moderate CYP3A4 inducers; appropriate medical judgement is required. Please contact Blueprint Medicines with any queries you have on this issue.

Source: [\(FDA, 2016\)](#)

**18.2 Appendix 2: List of Medications and Food to be Used with Caution****MEDICATIONS TO BE USED WITH CAUTION WITH AVAPRITINIB**

CYP3A4 Substrates	CYP2C9 Substrates	BCRP Substrates	Moderate CYP3A4
Inhibitors			
Alfentanil	Warfarin	Rosuvastatin	Erythromycin
Cyclosporine	Phenytoin	Methotrexate	Fluconazole
Dihydroergotamine		Lapatinib	Crizotinib
Ergotamine			Dronedarone
Fentanyl			Imatinib
Midazolam			Diltiazem
Pimozide			
Quinidine			
Simvastatin			

Sirolimus  
Tacrolimus  
Terfenadine

Abbreviations: BCRP = Breast Cancer Resistance Protein; CYP3A4 = Cytochrome P450 3A4; CYP2C9 = cytochrome P450 2C9

This list is not intended to be exhaustive. A similar restriction will apply to other drugs that are sensitive substrates of CYP3A4, CYP2C9, or BCRP, and moderate inhibitors of CYP3A4; appropriate medical judgement is required. Please contact Blueprint Medicines with any queries you have on this issue.

Source: ([FDA, 2016](#))

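### The concomitant-medication rules conflict on CYP3A4 inducers: Sections 5.4.1–5.4.3 leave them unprohibited, Appendix 1 excludes them, and phenytoin carries two statuses

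*Combined protocol and SAP*

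**What the plan says.** Five places in the protocol bear on this point.

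- **Section 5.4.1 (prohibited).** "Concomitant treatment with drugs that are strong CYP3A4 inhibitors are prohibited", with a pointer to Appendix 1 for the list of strong inhibitors. The section also restricts other cancer treatment: "Avapritinib should not be administered simultaneously with other antineoplastic therapy". It asks for an interruption around radiotherapy. Inducers do not appear.
- **Section 5.4.2 (caution).** "Medications that are CYP2C9, CYP3A4, or BCRP substrates with a narrow therapeutic index should be used with caution", with a pointer to Appendix 2. Drugs known to raise seizure risk are added as a second class.
- **Section 5.4.3 (permitted).** Anything outside what 5.4.1 and 5.4.2 specify is allowed, "including palliative and supportive care for disease-related symptoms are permitted". The appendices are not mentioned.
- **Section 4.4, exclusion 1 (entry).** "Patient requires therapy with a concomitant medication that is a strong inhibitor or strong inducer of cytochrome P450 (CYP) 3A4", with a reference to Section 5.4.1. Moderate inducers are not mentioned.
- **Appendices 1 and 2.** Appendix 1 is headed "EXCLUDED MEDICATIONS AND FOODS FOR PATIENTS RECEIVING" avapritinib and has columns for strong inhibitors, strong inducers and moderate inducers. Its footnote reads: "A similar restriction will apply to other drugs that are known to strongly modulate CYP3A4 via inhibition or induction or are moderate CYP3A4 inducers". Appendix 2 is the caution list and has a column for moderate CYP3A4 inhibitors. Its footnote reads: "A similar restriction will apply to other drugs that are sensitive substrates of CYP3A4, CYP2C9, or BCRP, and moderate inhibitors of CYP3A4".

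**The concern.** The protocol gives three different scopes for CYP3A4 modulators and a default rule that turns the narrowest one into permission. If 5.4.3 did not exist, silence on inducers in 5.4.1 could be read as an oversight that the appendix repairs. Because 5.4.3 permits what the two preceding sections do not specify, the silence has an effect.

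The practical question is what happens when a patient already on study is prescribed an inducer. Section 3.1 sets no maximum treatment duration, so co-medication can begin long after exclusion 1 was applied. The drug would be recorded (Section 6.2.5; Table 1, footnote k), but the text does not settle whether its use breaches the protocol. Two sites could handle the same prescription differently. The patient would carry any interaction risk that Appendix 1 was meant to avoid. Section 12 describes routine monitoring by phone or email, and its listed topics do not name concomitant medication, so the written rule has to do most of the work.

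**Working it through.** No statistical formula applies, because the protocol tests no hypothesis. The check sets the passages side by side and then counts the listed items affected.

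**Step 1. Status of each class by place in the protocol**

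| Class | Exclusion 1 (entry) | 5.4.1 | 5.4.2 | Default under 5.4.3 | Appendices |
|---|---|---|---|---|---|
| Strong CYP3A4 inhibitors | Barred | Prohibited | – | – | Excluded (App. 1) |
| Strong CYP3A4 inducers | Barred | Not named | Not named as a class | Permitted | Excluded (App. 1) |
| Moderate CYP3A4 inducers | Not named | Not named | Not named as a class | Permitted | Excluded (App. 1) |
| Moderate CYP3A4 inhibitors | Not named | Not named | Not named as a class | Permitted | Caution (App. 2) |

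Only the first row is consistent throughout. Rows two and three are direct on-treatment conflicts. The fourth is a milder mismatch between 5.4.2 and the list it cites.

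**Step 2. Does the pointer in 5.4.1 bring in the inducer columns?** It does not. It refers the reader to Appendix 1 for the strong inhibitors only.

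**Step 3. Count of Appendix 1**

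- Strong inhibitors 17, strong inducers 5, moderate inducers 5: 17 + 5 + 5 = 27.
- Inducers, the class 5.4.1 does not name: 5 + 5 = 10; 10/27 = 37.0%.
- Setting aside dabrafenib, if it falls under the antineoplastic restriction in 5.4.1: 10 − 1 = 9; 9/27 = 33.3%.
- Setting aside phenytoin as well, which reaches caution status through 5.4.2 and Appendix 2: 9 − 1 = 8; 8/27 = 29.6%.
- The 8 are carbamazepine, rifampin, St. John's Wort and phenobarbital (strong), and bosentan, efavirenz, etravirine and modafinil (moderate). None is named in 5.4.1, 5.4.2 or the Appendix 2 list.
- Exclusion 1 reaches the 4 strong inducers at entry only. For the 4 moderate inducers, Appendix 1 is the only place that bars them.

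**Step 4. Count of Appendix 2 and overlap**

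- CYP3A4 substrates 12, CYP2C9 substrates 2, BCRP substrates 3, moderate CYP3A4 inhibitors 6: 12 + 2 + 3 + 6 = 23.
- Items in both appendices: 1, phenytoin (strong CYP3A4 inducer in Appendix 1, CYP2C9 substrate in Appendix 2).
- Moderate inhibitors whose class 5.4.2 does not name: 6. If imatinib and crizotinib count as antineoplastic therapy under 5.4.1, 6 − 2 = 4 have no body-text rule for their class.

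**Step 5. Cross-reference.** Exclusion 1 sends the reader to 5.4.1 for a criterion that covers strong inducers. Section 5.4.1 contains nothing on inducers, so the reference is only half satisfied.

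**The case against.** The strongest reply is that the conflict is one of drafting and unlikely to mislead. A site that follows 5.4.1 to Appendix 1 finds all three columns under one heading of exclusion, a footnote that extends the restriction to moderate inducers, and an invitation to put queries to the sponsor. About 5 patients are expected, all previously treated with avapritinib in a trial. This limits how often the problem will arise. It does not remove it: a reader who sees both texts finds a conflict with nothing to say which prevails, and a reader who relies on 5.4.3 has no reason to ask.

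Several narrower objections have force.

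- **Percentages.** Both appendices say they are not exhaustive, so the shares describe printed lists, not patients exposed. A drug that is not named may also fall in one of the caution classes of 5.4.2. That would yield caution at most, which still differs from exclusion.
- **Exclusion 1.** It is an entry rule and can coexist with a broader on-treatment list. Its clear defect is the cross-reference.
- **Phenytoin.** It is listed for two different properties, and one could read the stricter entry as governing. The protocol states no such rule, so a site has two instructions for one drug.
- **Moderate inhibitors.** Permitted and use-with-caution are compatible, so this is incomplete wording in 5.4.2 and not a contradiction.
- **Withdrawal.** Section 4.6 lists protocol deviation as an optional reason for withdrawal from treatment, but investigator decision is on the same list. Unclear deviation status therefore changes little about whether a patient can be withdrawn.
- **Harm.** The concomitant-therapy sections and appendices do not give the size or direction of an inducer interaction, so harm cannot be quantified from them.

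**Conclusion.** The concern holds. Sections 5.4.1 and 5.4.3, read literally, permit on-treatment use of CYP3A4 inducers that Appendix 1 excludes. This is a contradiction in the current text, not a missing detail. The faulty cross-reference in exclusion 1, the double status of phenytoin and the gap on moderate inhibitors are secondary mismatches of the same kind.

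The conflict covers two of the three columns of Appendix 1: 10 of 27 listed items, 9 without dabrafenib, and 8 with no named status elsewhere in 5.4.1, 5.4.2 or Appendix 2. These counts rest on the printed lists and on the assumption that dabrafenib, imatinib and crizotinib are antineoplastic therapy; results are shown with and without that assumption. There is no effect on sample size or error rates, and the small number of patients limits the practical reach. The point should be corrected, but it does not threaten the study's objectives.

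**What to change.** Amend exclusion 1, Sections 5.4.1–5.4.3 and Appendices 1 and 2 together, so that:

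1. each CYP3A4 class (strong inhibitors, strong inducers, moderate inducers, moderate inhibitors) has one stated on-treatment status in both the body text and the appendices, and any intended difference between the entry rule and the on-treatment rule is stated;
2. phenytoin has a single status, or the protocol says which entry governs when a drug is on both lists;
3. the reference from exclusion 1 to 5.4.1, and those from 5.4.1 and 5.4.2 to the appendices, point to text that covers the classes named;
4. the default in 5.4.3 refers to the appendices as well as to 5.4.1 and 5.4.2.

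Which status each class or drug should have is for the sponsor to decide; this review takes no position on it. The cost is a wording amendment with the ethics committee submission and approval that Section 13 requires. It adds no procedures, visits or patients.
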